3.9 Safety evaluation

For all safety analyses, the safety set will be used. The assessment of safety will be based mainly on the frequency of adverse events and on the number of laboratory values that fall outside of pre-determined ranges.

The overall observation period will be divided into three mutually exclusive segments:

- pre-treatment period: from day of patient's informed consent to the day before first dose of study treatment
- on-treatment period: from day of first dose of study medication to 30 days after last dose of study treatment
- post-treatment period: starting on day 31 after last dose of study treatment.

Safety summary tables will only include on-treatment events/assessments, i.e., those collected no later than 30 days after the date of the last study treatment administration. All safety events/assessments will be listed and those collected in the pre- and post-treatment period will be flagged.

3.9.1 Adverse events (AEs)

3.9.1.1 Coding of AEs

Adverse events are coded using the Medical Dictionary for Regulatory Activities (MedDRA) terminology.

3.9.1.2 Grading of AEs

AEs will be graded according to the Common Terminology Criteria for Adverse Events (CTCAE) version 4.03.

The CTCAE represents a comprehensive grading system for reporting the acute and late effects of cancer treatments. CTCAE v4.03 grading is by definition a 5-point scale generally corresponding to mild, moderate, severe, life threatening, and death. This grading system inherently places a value on the importance of an event, although there is not necessarily proportionality among grades (a grade 2 AE is not necessarily twice as severe as a grade 1 AE).

If CTCAE grading does not exist for an adverse event, grades 1 – 4 corresponding to the severity of mild, moderate, severe, and life-threatening will be used. CTCAE grade 5 (death) will not be used in this study; rather, this information will be collected on the “End of Treatment”, “Study Evaluation Completion” or “Survival Information” eCRF pages.

3.9.1.3 General rules for AE Reporting

AE summaries will include all AEs starting on or after study day 1 (i.e., on or after the day of the first intake of study treatment) and starting no later than 30 days after the last treatment/exposure date. All AEs will be listed. AEs starting prior to study day 1 and AEs starting later than 30 days after the last treatment/exposure date will be flagged in the listings.

AEs will be summarized by presenting the number and percentage of patients having at least one AE, and having at least one AE in each body system/primary system organ class (SOC_TXT), and for each preferred term (PT_TXT) using MedDRA coding. A subject with multiple occurrences of an AE will be counted only once in the AE category.

Separate AE summaries will be presented by primary system organ class, preferred term, and maximum CTC grade (AEVGRD1C). A patient with multiple CTC grades for an AE will be summarized under the maximum CTC grade recorded for the event. In the summaries presented by grade, all AEs will be pooled regardless of whether they are CTC gradable or not, i.e., regardless of whether the question “CTC AE” (variable CTIAEV1C) on the Adverse Events eCRF is answered ‘Yes’ or ‘No’.

The frequency of CTC grade 3 and 4 AEs will be summarized separately.

Any information collected (e.g., CTC grades, relatedness to study drug, action taken, etc.) will be listed as appropriate.

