#### 10.5.3.2 Adverse events (AEs)

All adverse events recorded during the study will be summarized. The incidence of treatment-emergent AEs, i.e., AEs that started or worsened during the on-treatment period, will be summarized by system organ class, preferred term, severity (based on CTCAE grades), type of adverse event and relation to the study drug by treatment group. Deaths reportable as severe adverse events (SAEs) and non-fatal SAEs will be listed by patient and tabulated by type of adverse event and treatment group. All AEs (including those from the pre- and post-treatment periods) will be listed and those collected during the pre- and post-treatment period will be flagged.

Adverse events will be summarized by presenting the number and percentage of patients having any adverse event in each body system and having each individual adverse event. Any other information collected (e.g., severity or relatedness to study medication) will be listed as appropriate.

In addition, adverse events of related nature and/or for which there is a specific clinical interest in connection with the study treatments may be analyzed by categories regrouping the relevant preferred terms, as appropriate. For each such category, the number and percentage of patients with at least one AE belonging to the category will be reported.

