2.1.8 On-treatment assessment/event

Safety summaries and selected summaries of deaths will summarize only on-treatment assessments/events. On-treatment assessment/event is defined as any assessment/event obtained in the time interval:

[date of first administration of study treatment; date of last administration of study treatment + 30 days], i.e., including the lower and upper limits. (Note: The calculation of study treatment duration, however, may use different rules as specified in [Section 3.6.1.](#))

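### SAP 3.9.1.3 admits AEs to the summary tables by start date alone, which is narrower than the protocol's started-or-worsened definition of treatment-emergent AEs

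*SAP*

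**What the plan says.** Protocol 10.5.3.2 opens broadly: "All adverse events recorded during the study will be summarized". It then says that the incidence of treatment-emergent events will be tabulated by organ class, preferred term, severity, type and relation to drug, and defines these as "AEs that started or worsened during the on-treatment period". Events from before and after the on-treatment period are to be listed and flagged.

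SAP 3.9.1.3 sets the rule that the programmer will follow: "AE summaries will include all AEs starting on or after study day 1", meaning the day of first intake, and "starting no later than 30 days after the last treatment/exposure date". AEs with an earlier or later start are listed and flagged.

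Two other SAP sections bear on this. SAP 3.9 states that "Safety summary tables will only include on-treatment events/assessments". SAP 2.1.8 gives the window: "On-treatment assessment/event is defined as any assessment/event obtained in the time interval" running from first dose to 30 days after last dose. Neither mentions worsening. The SAP change history records edits to sections 3.9.1.2, 3.9.1.4, 3.9.1.6 and 3.9.2, but none that narrows the treatment-emergent definition or gives a reason for doing so.

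**The concern.** AEs are collected from informed consent (protocol 7.2.2.1 and 8.1.1), while dosing can follow up to about four weeks later. An event can therefore begin at low grade in screening and become severe on drug. Under the protocol that is treatment-emergent. Under the SAP it is judged by its onset and can fall outside the AE tables. Safety is a secondary objective, and the SAP says its assessment rests mainly on AE frequency, so the rule deciding which AEs are counted should be the protocol's rule or a justified departure from it.

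The direction is fixed. Every AE the SAP admits is also admitted by the protocol, but not the reverse, so against the protocol definition the SAP can only undercount. Randomization is at the Day 1 visit, so onset before first dose mostly precedes randomization and should be similar across arms. Later worsening need not be similar.

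**Working it through.** The documents give no figure to reproduce, so the check applies both rules to each way an event can arise.

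**Inputs**
- Protocol rule (10.5.3.2): started or worsened during the on-treatment period.
- SAP rule (3.9.1.3): start date from first intake to 30 days after last exposure.
- Exposed window: screening within 28 days before first dose (protocol 4.1.1). It can be longer after re-screening, which needs no new consent (protocol 7.1.1.1).
- Recording: AEs that begin or worsen after consent go on the AE page (protocol 8.1.1). Severity is reassessed at each visit, but how a change is entered is not stated.

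**The two rules, case by case**

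| Case | Protocol | SAP tables |
|---|---|---|
| (a) AE starts on or after first dose | in | in |
| (b) Condition present at consent worsens on drug, entered as an AE dated at worsening | in | in |
| (c) AE starts between consent and first dose, worsens on drug, new dated record | in | in |
| (d) As (c), but kept on one record with its pre-dose start date | in | out; listed and flagged |

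The rules differ in case (d), and for the same reason in case (b) if the AE carries a date before day 1. SAP 3.9.1.3 does take the maximum grade when one AE has several, but only for AEs that have already passed the start-date filter.

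**Which outputs are touched.** These are the AE incidence tables in SAP 3.9.1.4: overall, suspected-related, by maximum grade, grade 3/4, serious, leading to discontinuation, and requiring dose adjustment or interruption. Laboratory tables use worst post-baseline grade and shifts from baseline (SAP 3.9.2). Vital signs (3.9.3), deaths and disposition (3.5) do not depend on an AE start date. One visible result could be a patient counted under adverse event as the reason for stopping in the disposition table, but absent from the table of AEs leading to discontinuation.

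**Rough size, on assumed rates only.** Protocol Amendment 3 gives 309 randomized, so 309 / 3 = 103 per arm on average; the Safety Set may differ slightly. Assume 5% to 15% of patients have an AE starting before first dose, that a quarter of these worsen on drug, and that all are kept on one record:
- low: 103 × 0.05 × 0.25 = 1.3 patients per arm
- high: 103 × 0.15 × 0.25 = 3.9 patients per arm

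One patient is 1 / 103 = 1.0 percentage point in a table row. If every grade change opens a new dated record, the count is 0.

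**The case against.** The strongest reply is that case (d) may not occur. The protocol counts the worsening of an existing condition as an AE in its own right, so a worsening on drug can be read as a new event starting on the day it worsened. It asks for a severity grade and start and end dates for each AE, which fits one grade per dated record. SAP 3.9.1.6 foresees consecutive AEs with the same term and differing severity and merges those separated by at most one day, a rule that is useful if worsening does open new records. Under that convention the two rules give the same tables.

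This stands as a limit on the point, but it does not dispose of it. Protocol 7.2.2.1 and 8.1.1 also describe following one event to resolution while noting changes in its severity, and SAP 3.9.1.3 allows several grades within one AE. The merging rule in 3.9.1.6 serves only the disclosure tables. Neither document states the eCRF convention.

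A reader might infer that these events vanish from every safety table. The documents do not support that: the start-date rule governs AE summaries only, and all AEs remain in the listings. Nor do they support assuming that the loss is certain or that it falls mainly on higher grades.

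It is also fair to say that a remedy may not be derivable from the data. If only a maximum grade is held for each record, an on-treatment increase cannot be dated.

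**Conclusion.** The mismatch is real: the SAP does not implement the protocol's definition and does not say why. Its effect is confined to the AE incidence tables in SAP 3.9.1.4, and to events that start between consent and first dose, worsen on drug and stay on a record dated before day 1. The documents contain no count of such events. On the assumed rates it is a few patients per arm at most, spread over many preferred terms, so a typical row would move by 0 or 1 patient. A patient leaves the any-AE row only if she has no other on-treatment AE. No efficacy result is involved. Severity: minor.

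**What to change.** Amend SAP 3.9.1.3 so that AE summaries include AEs that start, or that started before day 1 and increase in grade, between the first dose and 30 days after the last dose. Apply this to the AE tables in 3.9.1.4. State how the eCRF records a change in grade.

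If no dated grade history is stored, report by arm the number of AEs with onset before day 1 that were ongoing at first dose, with their maximum grade. That shows how many events are at issue without assuming when they worsened.

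The cost is one clause, a small derivation change and slightly higher AE counts. The SAP's Addendum 1, dated after database lock, already revised the capecitabine exposure derivation, so a change of this kind has a precedent in the trial.

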3.9.1.4 AE summaries

The following adverse event summaries will be produced:

- Adverse events, regardless of study drug relationship by primary system organ class and preferred term
- Adverse events with suspected relationship to study drug by primary system organ class, preferred term
- Adverse events with an overall incidence rate of 5% or more in either treatment arm, regardless of study drug relationship by primary system organ class and preferred term
- Adverse events, regardless of study drug relationship by primary system organ class, preferred term and maximum CTC
- Adverse events with suspected study drug relationship by primary system organ class, preferred term and maximum CTC
- CTC grade 3 or 4 adverse events, regardless of study drug relationship by primary system organ class and preferred term
- CTC grade 3 or 4 adverse events with suspected study drug relationship by primary system organ class and preferred term
- Deaths, by primary system organ class and preferred term
- On-treatment deaths, by primary system organ class and preferred term
- Serious adverse events, regardless of study drug relationship, by primary system organ class and preferred term
- Serious adverse events with suspected study drug relationship, by primary system organ class and preferred term
- Adverse events leading to study drug discontinuation, regardless of study drug relationship, by primary system organ class and preferred term
- Adverse events requiring dose adjustment or study-drug interruption, regardless of study drug relationship, by primary system organ class and preferred term
- Adverse events requiring additional therapy, regardless of study drug relationship, by primary system organ class and preferred term
- All grade 3/4 non-hematological adverse events

3.9.1.5 AEs of special interest (AESIs)

Specific groupings of adverse events (AESIs) will be considered and the number of patients with at least one event in each grouping will be reported for the entire population. Such groups consist of adverse events for which there is a specific clinical interest in connection with RAD001 treatment (i.e. where RAD001 may influence a common mechanism of action responsible for triggering them) or adverse events which are similar in nature (although not identical). The latest version of Case Retrieval Strategy (CRS) sheet should be used.

3.9.1.6 Clinical trial safety disclosure

For the legal requirements of ClinicalTrials.gov and EudraCT, two required tables on on-treatment adverse events which are not serious adverse events with an incidence greater than 5% and on on-treatment serious adverse events and SAE suspected to be related to study treatment will be provided by system organ class and preferred term on the safety set population.

If for a same patient, several consecutive AEs (irrespective of study treatment causality, seriousness and severity) occurred with the same SOC and PT:

- a single occurrence will be counted if there is ≤ 1 day gap between the end date of the preceding AE and the start date of the consecutive AE
- more than one occurrence will be counted if there is > 1 day gap between the end date of the preceding AE and the start date of the consecutive AE

For occurrence, the presence of at least one SAE / SAE suspected to be related to study treatment / non SAE has to be checked in a block e.g., among AE's in a ≤ 1 day gap block, if at least one SAE is occurring, then one occurrence is calculated for that SAE.

The number of deaths resulting from SAEs suspected to be related to study treatment and SAEs irrespective of study treatment relationship will be provided by SOC and PT.

3.9.2 Laboratory data

All laboratory values will be converted into SI units and the severity grade calculated using appropriate common toxicity criteria (CTCAE).

A listing of laboratory values will be provided by laboratory parameter, patient, and treatment group. A separate listing will display notable laboratory abnormalities (i.e., newly occurring CTCAE grade 3 or 4 laboratory toxicities). The frequency of laboratory abnormalities will be displayed by parameter and treatment group.

Laboratory data summaries will include all laboratory assessments collected no later than 30 days after the last treatment/exposure date. All laboratory assessments will be listed and those collected later than 30 days after the last treatment/exposure date will be flagged in the listings.

Laboratory data will be classified (by Novartis biostatistics/SAS programming) into CTC grades according to the NCI Common Terminology Criteria for Adverse Events (CTCAE) v4.03. A severity grade of 0 will be assigned when the value is within normal limits. In the case when a local laboratory normal range overlaps into the higher (i.e., non-zero) CTC grade, the laboratory value will still be taken as within normal limits and assigned a CTC grade of zero.

The following rules will be applied:

- Conflict between normal range and grade definition: because many institutions have differences for normal ranges of metabolic laboratory and hematology values, the CTCAE often uses the terms 'Upper Limit of Normal (ULN)' and 'Lower Limit of Normal (LLN)' in lieu of actual numerical values. In some cases, an institution's LLN might be beyond the range specified for a grade. In this case, the institutional limits of normal should take precedence over the CTCAE values: the laboratory value will still be taken as within normal limits and assigned a CTC grade of zero.
- For the few parameters having comparison to baseline in CTCAE grading definition (Fibrinogen, INR, Hemoglobin, Creatinine), the highest grade will be retained. In other words, in the particular case when a value is grade x as per CTC grade definition based on threshold/ranges and also grade x+1 when comparing to baseline, grade x+1 is retained.

- Grade 5 will not be used. Grade values will be integers from -4 to 4.
- For calcium, CTCAE grading is based on Corrected Calcium and not on Calcium. Corrected Calcium (CALC) will be calculated from Albumin and Calcium: Corrected Calcium (mg/dL) = Calcium (mg/dL) -0.8 [Albumin (g/dL)-4].
- GFR will be calculated based on creatinine (CREA parameter) collected regularly during treatment and the CTC grade will be determined for GFR.
- For creatinine clearance (CRCLCG parameter), no calculation of CTC grade will be done.

The following summaries will be produced for the laboratory data (by laboratory parameter and treatment):

- Number and percentage of patients with worst post-baseline CTC grade (regardless of the baseline status). Each patient will be counted only for the worst grade observed post-baseline.
- Shift tables using CTC grades to compare baseline to the worst post-baseline value will be produced for hematology and biochemistry laboratory parameters with CTC grades.
- For laboratory parameters where CTC grades are not defined, shift tables to the worst post-baseline value will be produced using the low/normal/high classifications based on laboratory reference ranges.

The following listings will be produced for the laboratory data:

- Listing of patients with laboratory values outside the laboratory reference ranges with values flagged to show the corresponding CTC grades and the classifications relative to the laboratory reference ranges.
- Listing of all laboratory data with values flagged to show the corresponding CTC grades and the classifications relative to the laboratory reference ranges.

3.9.3 Vital signs

Vital sign assessments will be performed in order to characterize basic body function. The parameters expected to be collected include: height (cm), weight (kg), body temperature (°C), pulse rate (beats per minute), systolic and diastolic blood pressure (mmHg).

The criteria for clinically notable abnormalities are defined as follows:

Clinically notable elevated values

- systolic BP: ≥ 180 mmHg and an increase ≥ 20 mmHg from baseline
- diastolic BP: ≥ 105 mmHg and an increase ≥ 15 mmHg from baseline
- body temperature: $\geq 39.1^{\circ}\text{C}$
- weight: increase from baseline of $\geq 10\%$
- pulse rate: ≥ 120 bpm with increase from baseline ≥ 15 bpm

Clinically notable below normal values

- systolic BP: ≤ 90 mmHg and a decrease ≥ 20 mmHg from baseline
- diastolic BP: ≤ 50 mmHg and a decrease ≥ 15 mmHg from baseline

- body temperature: $\leq 35^{\circ}\text{C}$
- weight: decrease from baseline of $\geq 10\%$
- pulse rate: ≤ 50 bpm with decrease from baseline ≥ 15 bpm.

The following summaries will be produced for each vital sign parameter:

- summary statistics for change from baseline to the worst post-baseline value (in both directions, i.e., from baseline to the highest post-baseline and from baseline to the lowest post-baseline value)
- number and percentage of patients with at least one post-baseline vital sign abnormality (in both directions, i.e., both elevated and below normal values).

In addition, the following two listings will be produced by treatment group:

- patients with clinically notable vital sign abnormalities
- all vital sign assessments will be listed by patient and vital sign parameter.

[figure not shown]
In both listings, the clinically notable values will be flagged and also the assessments collected later than 30 days after the last treatment/exposure date will be flagged.

3.9.4 Other safety data

Data from other tests (e.g., electrocardiogram, pulmonary function tests, LVEF) will be listed, notable values will be flagged, and any other information collected will be listed as appropriate.

All assessments collected later than 30 days after the last treatment/exposure date will be flagged in the listings.

Any statistical tests performed to explore the data will be used only to identify any interesting comparisons that may warrant further consideration.

3.11 Interim analysis

One efficacy interim analysis of PFS was conducted to allow early termination of the everolimus monotherapy arm, in case of far inferior efficacy as compared to the everolimus + exemestane combination treatment arm. The efficacy interim analysis was planned after 75 PFS events have been observed as per local tumor assessment, across the following 2 arms: everolimus monotherapy and everolimus + exemestane combination arm.

Based on simulations, the probability of stopping the everolimus monotherapy arm was calculated.

Table 3-2 Probability (from 2000 simulated trials) of stopping a single agent arm under different truth

True hazard ratio	Probability of stopping everolimus monotherapy arm at 75 PFS events
0.1	99.30%
0.2	48.75%
0.3	6.45%
0.4	0.5%
0.5	0%

A general guidance was to stop the single agent arm if the observed hazard ratio was less than 0.20, (i.e., if the everolimus monotherapy arm was far inferior when compared to the everolimus + exemestane combination arm). The proposed decision guidance yielded high probability to stop the control arm if the combination arm is highly superior ($HR \leq 0.1$), while keeping the probability low if the superiority was not so extreme ($HR \geq 0.3$).

At the time of interim analysis, the observed hazard ratio along with the 90% confidence interval was provided for decision making. Simulation (L.J. Wei, 2007) was also carried out to predict the hazard ratio and 90% confidence interval at the final analysis, based on the data observed at interim.

The predicted hazard ratios and 90% confidence intervals were provided by the independent statistician to independent programmer as per following process:

- Trial statistician created R program that was used to calculate predicted hazard ratios and 90% confidence intervals and put this program into GPS under source control in the unrestricted area.
- Independent statistician imported this R program in the restricted area, put it under source control and used it to produce a csv file in the restricted area containing the predicted hazard ratios and 90% confidence intervals.
- Independent programmer used the csv file created by independent statistician to produce outputs displaying the predicted hazard ratios and 90% confidence intervals.

Based on the interim analysis results and DMC recommendation, the study continues without change.

